11.6. Appendix 6: Premature Withdrawals & Handling of Missing Data

11.6.1. Premature Withdrawals

Element	Reporting Detail
General	
 • As defined in the protocol the overall study duration for each participant is 36 months (up to 36 months including the screening period). • Primary study completion for each participant will be at 24 months when all available data will be analysed. • Participant study completion is defined as participants who either prematurely withdrawn or: 
 ○ Patients who had yet to complete their Month 24 visit at the time of approval of Protocol Amendment 9, will be defined as completed if they complete the Month 24 Visit.

Element	Reporting Detail
	
 Patients past Month 24 visit at time of approval of Protocol Amendment 9 will be followed up with a final communication or visit (final follow up) and will be defined as completors if they have completed this follow-up visit. Withdrawn participants maybe replaced in the study. All available data from participants who were withdrawn from the study will be listed and all available planned data will be included in summary tables and figures, unless otherwise specified. If data is present after the participants withdrawal from treatment date, this data will be flagged in the listings.

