3.3.1.2. Study Duration

Data from the literature at the origin of the study design identified a causal relationship between the degree of immunosuppression and an increased incidence of EBV related Post Transplant Lymphoproliferative Disorders (PTLD) and for this reason a long-term follow-up (60 months) was implemented at the start of the study. The interim analysis data which emerged from this study showed a prompt regain of immune competence observed in treated subjects and consequent rapid resolution of EBV reactivation, both clinically and virologically. The long term EBV related PTLTD risk, as observed in solid organ transplant on a chronic immune suppression therapy, is negligible. As a result, the overall study duration for each subject will be 24 months, except for those patients who have already passed the 24 month or 36 month follow up, in which case they will have a final follow up communication (telephone call or visit) as soon as possible following approval of this amendment 08 of the protocol. Further details are provided in the Study Reference Manual (SRM). If further follow up is required, the Investigator will request that the patient visits the site. See Section 9.3 for a description of analysis considerations.

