4.6. Patient Completion

A completed patient is one who has completed Month 24.

The end of the study is defined as the last patient's last visit Month 24 or at final follow-up.

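### SAP 11.6.1 defines study completion differently from protocol 4.6: it lists premature withdrawal as a form of completion and adds a follow-up condition for patients already past Month 24

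*SAP*

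**What the plan says.** Protocol section 4.6 gives a single criterion at patient level: "A completed patient is one who has completed Month 24". It defines the end of the study separately, as the last patient's Month 24 visit or final follow-up. Protocol section 3.3.1.2 sets the duration: "the overall study duration for each subject will be 24 months, except for those patients who have already passed the 24 month" or Month 36 point, who have one final contact after Amendment 08 is approved.

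SAP section 11.6.1 covers the same ground differently:

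- Duration: "As defined in the protocol the overall study duration for each participant is 36 months", with the same figure repeated for the period including screening.
- Lead-in to the completion rule: "Participant study completion is defined as participants who either prematurely withdrawn or", followed by two sub-bullets.
- First sub-bullet, for patients who had not yet reached Month 24: "at the time of approval of Protocol Amendment 9, will be defined as completed if they complete the Month 24 Visit".
- Second sub-bullet, for patients already past Month 24, who are to have a final communication or visit: they "will be defined as completors if they have completed this follow-up visit".

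The output that depends on this is Table 1.01 (SAP section 11.10.4), the disposition summary based on the subject conclusion record.

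**The concern.** A disposition table is read against the protocol's meaning of a completer. Two parts of the SAP rule depart from that meaning. The lead-in makes withdrawal one of the alternatives under completion. The second sub-bullet adds a condition that the protocol does not set for the individual patient.

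I found no other completion definition in the SAP that would override this one. SAP section 2.1 records no change from the planned statistical analysis in the 26 October 2017 protocol. It does not mention completion status, so the difference is not documented as a deliberate departure either.

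What is at stake is descriptive: whether the completed and withdrawn counts by arm mean what the protocol says they mean. In arms this small, a reader will notice a shift of one patient.

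**Working it through.** The plan states no figure that can be reproduced here. The check is to apply both definitions to each kind of patient.

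| Patient | Protocol 4.6 | SAP 11.6.1 |
|---|---|---|
| Not yet at Month 24 when the amendment was approved; later attends Month 24 | Completer | Completer (first sub-bullet) |
| Withdraws before Month 24 | Not a completer | Placed under study completion by the lead-in; meets neither visit condition |
| Attended Month 24 before approval; final follow-up done | Completer | Completer (second sub-bullet) |
| Attended Month 24 before approval; final follow-up missed | Completer | Not a completer (second sub-bullet) |

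The definitions agree in rows 1 and 3. In row 2 the SAP is internally unclear. In row 4 it contradicts the protocol outright. The two problems work in opposite directions: the lead-in, if programmed literally, can only add completers, while the follow-up condition can only remove them.

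**Accompanying labels.**

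- Duration: 36 months for each participant in SAP 11.6.1. Protocol 3.3.1.2 gives 24 months with an exception, and SAP 2.3 says the study was shortened to 24 months. The next bullet in 11.6.1 itself places primary completion at 24 months.
- Amendment: SAP 11.6.1 refers twice to Protocol Amendment 9. The protocol's revision history ends at Amendment No. 8, document 2011N129686_09, dated 26 October 2017. SAP section 1 lists that document as Amendment No. 8, and SAP 3.2 refers to Amendment 08. The 9 was probably taken from the document suffix. It should still be corrected, because approval of this amendment decides which sub-bullet applies to a patient.

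**Size of one misclassification (illustration).**

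- Active arm, assuming the planned 8 patients: 1/8 = 12.5 percentage points.
- Pooled placebo, assuming 2 patients in each of 3 filled cohorts: 2 × 3 = 6, so 1/6 = 16.7 percentage points.

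The documents do not give achieved arm sizes. SAP 2.3 says the stopping criteria were met in Cohort 3 and gives a total of about 32, so 8 and 6 are assumptions.

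**Reach.** The populations in SAP section 4 are defined by screening, randomisation, dosing, protocol compliance, full treatment or availability of multimer data. None uses completion. The MMRM in SAP 9.1.5.1 does not use it either, and 11.6.1 keeps all available planned data from withdrawn participants in the summaries unless otherwise specified.

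**The case against.** The strongest reply is that the lead-in is only clumsy. It probably means to list the ways in which participation ends. The words for a completed participant appear only in the two sub-bullets, each tied to a visit, and the same section goes on to treat withdrawn participants as a distinct group. Table 1.01 carries a programming note on the primary reason for withdrawal, and Listing 02 gives reasons for study withdrawal. Missing data are also visible without the disposition table: the efficacy shells EFF_T1 and EFF_T2 print the number of subjects with data at each visit, and missing C-peptide responder status is reported in the frequency tables.

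Most of this stands. A reader might infer from the lead-in that every arm will show 100% completion whatever the dropout. The documents do not support that. Withdrawals are planned to be reported, and a patient past Month 24 who neither withdrew nor had the final contact would meet none of the SAP's alternatives.

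It is also fair to say that 36 months has some basis. The protocol's exception covers patients past Month 36, and the schedule keeps a Month 36 contact where applicable. That does not make it the duration for each participant.

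The reply does not answer the second sub-bullet. The extra follow-up condition is clearly worded and differs in substance from protocol 4.6. A charitable reading of the lead-in leaves that conflict in place.

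**Conclusion.** The completion definition in SAP 11.6.1 is inconsistent with protocol 4.6 and should be corrected. The firm part is the follow-up condition, which reverses the status of any patient who completed Month 24 but missed the final contact. The lead-in is a drafting fault that could mislead a programmer. The duration and the amendment number are labelling slips.

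The consequence is limited to the completer and withdrawal counts in Table 1.01. A reader might go further and suppose that the efficacy or safety results are affected. They are not, because nothing in those analyses is conditioned on completion. The number of patients affected cannot be derived from the documents, which give no count of those past Month 24 or of those who missed the final contact. The 12.5 and 16.7 point figures show how sensitive small arms are. They are not evidence that anyone will be misclassified.

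**What to change.** In SAP 11.6.1:

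1. Define a completer as a participant who completed the Month 24 visit, as in protocol 4.6, whether that visit fell before or after approval of the amendment.
2. Remove premature withdrawal from the completion definition. If a definition of the end of participation is wanted, give it in a separate sentence.
3. Report whether the final follow-up contact took place as a separate line, for patients already past Month 24 only.
4. State the duration as 24 months, with the protocol's exception for patients already past Month 24 or Month 36.
5. Replace both references to Amendment 9 with Amendment 8 (document 2011N129686_09).

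This costs a few lines of SAP text and a matching check of the Table 1.01 programming. It needs no new data and leaves every planned model and population unchanged.

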11.6.2. Handling of Missing Data

Element	Reporting Detail
General	
 Missing data occurs when any requested data is not provided, leading to blank fields on the collection instrument : 
 These data will be indicated by the use of a "blank" in participant listing displays. Unless all data for a specific visit are missing in which case the data is excluded from the table. Answers such as "Not applicable" and "Not evaluable" are not considered to be missing data and should be displayed as such.
Outliers	
 Any participants excluded from the summaries and/or statistical analyses will be documented along with the reason for exclusion in the clinical study report.

11.6.3. Handling of Partial Dates

Element	Reporting Detail
Concomitant Medications	
 Partial dates for any concomitant medications recorded in the CRF will be imputed using the following convention: 
 If the partial date is a start date, a '01' will be used for the day and 'Jan' will be used for the month If the partial date is a stop date, a '28/29/30/31' will be used for the day (dependent on the month and year) and 'Dec' will be used for the month. The recorded partial date will be displayed in listings.
Adverse Events	
 Any partial dates for adverse events will be raised to data management. If the full date cannot be ascertained, the following assumptions will be made: 
 If the partial date is a start date, a '01' will be used for the day and 'Jan' will be used for the month. However, if these results in a date prior to Week 1 Day 1 and the event could possibly have occurred during treatment from the partial information, then the Week 1 Day 1 date will be assumed to be the start date. The AE will then be considered to start on-treatment (worst case). If the partial date is a stop date, a '28/29/30/31' will be used for the day (dependent on the month and year) and 'Dec' will be used for the month. The recorded partial date will be displayed in listings.

11.7. Appendix 7: Values of Potential Clinical Importance

11.7.1. Laboratory Values

Haematology				
Laboratory Parameter	Units	Category	Clinical Concern Range	
			Low Flag (< x)	High Flag (>x)
Basophiles	x10 ⁹ /L		0.02	0.1
Hematocrit	Ratio of 1		0.24	0.54
		Δ from BL	↓0.075	
Hemoglobin	g/dL		8	18
		Δ from BL	↓2.5	
Lymphocytes	x10 ⁹ /L		0.8	
Mean Corpuscular Volume (MCV)	fL		80	100
Mean Corpuscular Hemoglobin (MCH)	pg		27	33
Mean Corpuscular Hemoglobin Concentration (MCHC)	g/L		330	360
Monocytes	x10 ⁹ /L		0.2	1.0
Eosinophils	x10 ⁹ /L			0.44
Neutrophil Count	x10 ⁹ /L		1.5	
Platelet Count	x10 ⁹ /L		100	550
Red Blood Cell Count (RBC)	x10 ¹² /L		4.2	5.9
Reticulocyte Count	x10 ⁹ /L		23	90
While Blood Cell Count (WBC)	x10 ⁹ /L		3	20

Clinical Chemistry				
Laboratory Parameter	Units	Category	Clinical Concern Range	
			Low Flag (< x)	High Flag (>x)
Albumin	g/L		30	
Calcium	mmol/L		2	2.75
Creatinine	umol/L			1.3x ULN
		Δ from BL		↑ 44
Glucose	mmol/L		3	11.1
Potassium	mmol/L		3.2	5.5
Sodium	mmol/L		130	150

Liver Function			
Test Analyte	Units	Category	Clinical Concern Range

Liver Function			
Test Analyte	Units	Category	Clinical Concern Range
ALT/SGPT	IU/L	High	≥ 2x ULN
			≥ 3x ULN
AST/SGOT	IU/L	High	≥ 2x ULN
Alkaline Phosphatase	IU/L	High	≥ 1.5x ULN
			≥ 2x ULN
T Bilirubin	µmol/L	High	≥ 1.5xULN
T. Bilirubin + ALT	µmol/L	High	≥ 1.5xULN T. Bilirubin + ≥ 2x ULN ALT
	U/L		≥ 2xULN T. Bilirubin + ≥ 3x ULN ALT
Urea Nitrogen (BUN)	mmol/L	Low	< 2.9
		High	>7.1
Chloride	mmol/L	Low	< 98
		High	
		High	≥ 2x ULN
Direct Bilirubin	µmol/L	High	> 7.1
Urate	µmol/L	Low	< 150
		High	> 470
Total Protein	g/L	Low	< 60
		High	> 78

11.7.2. ECG

ECG Parameter	Units	Clinical Concern Range	
		Lower	Upper
Absolute			
Absolute QTc Interval	msec		>450
Absolute PR Interval	msec	< 110	> 220
Absolute QRS Interval	msec	< 75	> 120
Change from Baseline			
Increase from Baseline QTc	msec	>60	

11.7.3. Vital Signs

Vital Sign Parameter (Absolute)	Units	Clinical Concern Range	
		Lower	Upper
Systolic Blood Pressure	mmHg	< 85	> 160
Diastolic Blood Pressure	mmHg	< 45	> 100
Heart Rate	bpm	< 40	> 110
Respiration Rate	Min ⁻¹	< 10	> 30

11.8. Appendix 8: Biomarker Analyses

11.8.1. Handling of duplicate data due to reruns

Due to a rerun of samples from cohorts 1 and 2, duplicate data may be included in the SDTM data. For any such case, only the newer data will be used for summaries and the older data will only be included (with flag) in the listings.

11.8.2. Frequency and phenotype of lymphocyte subsets by flow cytometry

The list of analytes below will be summarised and analysed as per Section [9.4](#)

Lab Test (LBTEST)	Lab Test Code (LBTESTCD)	Units	Derived	Details
Lymphocytes	LYM	10 ⁹ /L		
CD3	CD3	10 ⁹ /L		CD3 T cells (10 ⁹ /L)
CD3/Lymphocytes	CD3LY	%		CD3 T cells
CD4	CD4	10 ⁶ /L		CD4 T cells (10 ⁶ /L)
CD4/Lymphocytes	CD4LY	%		CD4 T cells
CD8	CD8	10 ⁶ /L		CD8 T cells (10 ⁶ /L)
CD8/Lymphocytes	CD8LY	%		CD8 T cells
CD19	CD19	10 ⁹ /L		B cells (10 ⁹ /L)
CD19/Lymphocytes	CD19LY	%		B cells
CD4+CXCR3+CCR6-/CD4+	CDX5554	%		Th1
CD4+CXCR3+CCR6-	CDX555C	10 ⁶ /L	Yes	[CDX5554] x [CD4] / 100
CD4+CXCR3-CCR6-/CD4+	CDX5564	%		Th2
CD4+CXCR3-CCR6-	CDX556C	10 ⁶ /L	Yes	[CDX5564] x [CD4] / 100
CD4+CXCR3-CCR6+/CD4+	CDX5574	%		Th17
CD4+CXCR3-CCR6+	CDX557C	10 ⁶ /L	Yes	[CDX5574] x [CD4] / 100
CD4+CXCR3+CCR6+/CD4+	CDX5584	%		Th1 andTh17
CD4+CXCR3+CCR6+	CDX558C	10 ⁶ /L	Yes	[CDX5584] x [CD4] / 100
CD4+CD25+CD127-/CD4+	CDX5594	%		CD4 Tregs
CD4+CD25+CD127-	CDX559C	10 ⁶ /L	Yes	[CDX5594] x [CD4] / 100
CD8+CXCR3+CCR6-/CD8+	CDX5618	%		Tc1
CD8+CXCR3+CCR6-	CDX561C	10 ⁶ /L	Yes	[CDX5618] x [CD8] / 100
CD8+CXCR3-CCR6-/CD8+	CDX5628	%		Tc2
CD8+CXCR3-CCR6-	CDX562C	10 ⁶ /L	Yes	[CDX5628] x [CD8] / 100
CD8+CXCR3-CCR6+/CD8+	CDX5638	%		Tc17
CD8+CXCR3-CCR6+	CDX563C	10 ⁶ /L	Yes	[CDX5638] x [CD8] / 100
CD8+CXCR3+CCR6+/CD8+	CDX5648	%		Tc1/ Tc17
CD8+CXCR3+CCR6+	CDX564C	10 ⁶ /L	Yes	[CDX5648] x [CD8] / 100
CD8+CD25+CD127-/CD8+	CDX5668	%		CD8 Tregs
CD8+CD25+CD127-	CDX566C	10 ⁶ /L	Yes	[CDX5668] x [CD8] / 100
CD8+CD45RA-/CD8+	CDX5118	%		CD8 Memory
CD8+CD45RA+/CD8+	CDX1688	%		CD8 Naive
CD8-CD45RA-/CD8-	CDX601C8	%		CD4 Memory
CD8-CD45RA+/CD8-	CDX602C8	%		CD4 naïve

Lab Test (LBTEST)	Lab Test Code (LBTESTCD)	Units	Derived	Details
CD8 Memory Exhausted(CD45RA-CD8+)	CDX569J9	%		CD3+CD8+CD45RA-EOMES+ TIGIT+ KLRG1+ (% of CD45RA-CD8+)
CD8 Mem Exhausted IL-6R/CD8 Mem Exhaustd	CDX570K1	%		CD3+CD8+CD45RA-EOMES+ TIGIT+ KLRG1+ CD126+ (% of CD3+CD8+CD45RA-EOMES+ TIGIT+ KLRG1+)
CD8 Mem Exhausted IL-6R MNFI of CD126	CDX570J8	count		CD3+CD8+CD45RA-EOMES+ TIGIT+ KLRG1+ CD126+ (CD126 MFI)
CD3+CD8+CD126+/CD8+	CDX5678	%		CD8 IL-6R
CD3+CD8+CD126+ MNFI of CD126	CDX567J8	count		CD8 IL-6R
CD3+CD8-CD126+/CD8-	CDX568C8	%		CD4 IL-6R
CD3+CD8-CD126+ MNFI of CD126	CDX568J8	count		CD4 IL-6R
CD3+CD8+CD45RA+CD126+ MNFI of CD126	CDX571J8	count		CD8 naive IL-6R
CD3+CD8+CD45RA-CD126+ MNFI of CD126	CDX572J8	count		CD8 memory IL-6R
CD3+CD8-CD45RA+CD126+ MNFI of CD126	CDX573J8	count		CD4 naive IL-6R
CD3+CD8-CD45RA-CD126+ MNFI of CD126	CDX574J8	count		CD4 memory IL-6R

For ADLB PARAMCD will be set to be the same as LBTESTCD and PARAM will be set to LBTEST concatenated with the unit in brackets (in case of counts, no unit will be added).

11.8.3. Percentage of CD3 cells, FoxP3 regulatory cells and TH17 cells by epigenetic quantification

Lab Test (LBTEST)	Lab Test Code (LBTESTCD)	Units	Derived	Details
CD3+/Total Cells	CD3CE	%		
FoxP3/Total Cells	FOXP3CE	%		
T Helper 17 Cells/Total Cells	TH17CE	%		
FoxP3/CD3+	FOXP3CD3	%	Yes	= [FOXP3CE] x 100/[CD3CE]
T Helper 17 Cells/CD3+	TH17CD3	%	Yes	= [TH17CE] x 100/[CD3CE]

11.8.4. Frequency and phenotype of HLA-A2-restricted antigen-specific CD8+ T cells by multimer analysis

The data for the Frequency and phenotype of HLA-A2-restricted antigen-specific CD8+ T cells by multimer analysis will be reported only for the HLA-A2 Positive population.

Visits where the CD8 count is less 30,000 cells will be excluded from analysis and listed only except for EBV-specific CD8+ T cells for which counts less than 15,000 will be excluded from analysis and listed only. CD8 counts between 30,000 – 50,000 cells will be included in summaries but flagged in listings. Parameters will only be summarised if >40% of baseline visits and >40% of post-baseline visits are evaluable for that parameter.

The list of analytes below are for classification of participants and for determining the quality of cells, and hence will be listed only.

Lab Test (LBTEST)	Lab Test Code (LBTESTCD)	Units	Derived	Details
Viable Cells Count	VIABCC	Count		
Viable Cells/Total Cells	VIABCCE	%		
CD8+ Count	CD8C	Count		

The list of analytes below will be summarised and analysed as per Section 9.1.1.2.

Lab Test (LBTEST)	Lab Test Code (LBTESTCD)	Units	Derived	Details
T1D-specific CD8 T Cells/CD8+	T1D8CD8	%		
T1D-specific CD8 T Cells	T1DCD8	10 ⁶ /L	Yes	[T1D8CD8]*[CD8] / 100
Insulin B10-18-specific CD8 T Cells/CD8+	B1018C88	%		
Insulin B10-18-specific CD8 T Cells	B1018C8	10 ⁶ /L	Yes	[B1018C88] * [CD8] / 100
PPI-specific CD8 T Cells/CD8+	PPICD88	%		
PPI-specific CD8 T Cells	PPICD8	10 ⁶ /L	Yes	[PPICD88] * [CD8] / 100
Novel Insulin Epitope CD8 T Cells/CD8+	NINECD88	%		
Novel Insulin Epitope CD8 T Cells	NINECD8	10 ⁶ /L	Yes	[NINECD88] * [CD8] / 100
GAD65-specific CD8 T Cells/CD8+	GD65CD88	%		
GAD65-specific CD8 T Cells	GD65CD8	10 ⁶ /L	Yes	[GD65CD88] * [CD8] / 100
IGRP-specific CD8 T Cells/CD8+	IGRPCD88	%		
IGRP-specific CD8 T Cells	IGRPCD8	10 ⁶ /L	Yes	[IGRPCD88] * [CD8] / 100
IA2-specific CD8 T Cells/CD8+	IA2CD88	%		
IA2-specific CD8 T Cells	IA2CD8	10 ⁶ /L	Yes	[IA2CD88] * [CD8] / 100

Lab Test (LBTEST)	Lab Test Code (LBTESTCD)	Units	Derived	Details
pplAPP-specific CD8 T Cells/CD8+	PIAPCD88	%		
pplAPP-specific CD8 T Cells	PIAPCD8	10 ⁶ /L	Yes	[PIAPCD88] * [CD8] / 100
ZnT8-specific CD8 T Cells/CD8+	ZNT8CD88	%		
ZnT8-specific CD8 T Cells	ZNT8CD8	10 ⁶ /L	Yes	[ZNT8CD88] * [CD8] / 100
A2-specific CD8 T Cells/CD8+	A2CD8CD8	%		
A2-specific CD8 T Cells	A2CD8	10 ⁶ /L	Yes	[A2CD8CD8] * [CD8] / 100
EBV-specific CD8 T Cells/CD8+	EBVCD88	%		
EBV-specific CD8 T Cells	EBVCD8	10 ⁶ /L	Yes	[EBVCD88] * [CD8] / 100
CXCR3+ T1D-specific CD8 T Cells/CD8+	CDX5388	%		Migratory T1D-specific cells / total CD8 cells
CXCR3+ T1D-specific CD8 T Cells	CDX538C	10 ⁶ /L	Yes	[CDX5388] * [CD8] / 100
CCR7+CD45RA+ T1D CD8+ Cells/T1D CD8	CDX543J6	%		Naive T1D-specific cells / total T1D-specific cells
CCR7+CD45RA+ T1D CD8 T Cells	CDX543C	10 ⁶ /L	Yes	[CDX543J6] * [T1DCD8] / 100
CCR7+CD45RA- T1D CD8+ Cells/T1D CD8	CDX544J6	%		Central memory T1D-specific cells / total T1D-specific cells
CCR7+CD45RA- T1D CD8 T Cells	CDX544C	10 ⁶ /L	Yes	[CDX544J6] * [T1DCD8] / 100
CCR7-CD45RA- T1D CD8+ Cells/T1D CD8	CDX545J6	%		Effector T1D-specific cells / total T1D-specific cells
CCR7-CD45RA- T1D CD8+ T Cells	CDX545C	10 ⁶ /L	Yes	[CDX545J6] * [T1DCD8] / 100
CCR7-CD45RA+ T1D CD8+ Cells/T1D CD8	CDX546J6	%		Terminally differentiated effector memory T1D-specific cells / total T1D-specific cells
CCR7-CD45RA+ T1D CD8 T Cells	CDX546C	10 ⁶ /L	Yes	[CDX546J6] * [T1DCD8] / 100
CCR7+CD45RA+CXCR3+T1D CD8 T Cell/T1D CD8	CDX539J6	%		Migratory Naive T1D-specific cells / total T1D-specific cells
CCR7+ CD45RA+ CXCR3+T1D CD8 T Cell	CDX539C	10 ⁶ /L	Yes	[CDX539J6] * [T1DCD8] / 100
CCR7+CD45RA-CXCR3+ T1D CD8+ Cell/T1D CD8	CDX540J6	%		Migratory Central memory T1D-specific cells / total T1D-specific cells
CCR7+CD45RA-CXCR3+ T1D CD8 T Cells	CDX540C	10 ⁶ /L	Yes	[CDX540J6] * [T1DCD8] / 100
CCR7-CD45RA-CXCR3+ T1D CD8+ Cell/T1D CD8	CDX541J6	%		Migratory Effector T1D-specific cells / total T1D-specific cells
CCR7-CD45RA-CXCR3+ T1D CD8 T Cells	CDX541C	10 ⁶ /L	Yes	[CDX541J6] * [T1DCD8] / 100
CCR7-CD45RA+CXCR3+ T1D CD8+ Cell/T1D CD8	CDX542J6	%		Migratory Terminally differentiated effector memory T1D-specific cells / total T1D-specific cells
CCR7-CD45RA+CXCR3+	CDX542C	10 ⁶ /L	Yes	[CDX542J6] * [T1DCD8] / 100

Lab Test (LBTEST)	Lab Test Code (LBTESTCD)	Units	Derived	Details
T1D CD8 T Cells				
CCR7+CD45RA+ EBV CD8+ Cells/EBV CD8	CDX551J7	%		Naive EBV -specific cells / total EBV-specific cells
CCR7+CD45RA+ EBV CD8 T Cells	CDX551C	10 ⁶ /L	Yes	[CDX551J7] * [EBVCD8] / 100
CCR7+CD45RA- EBV CD8+ Cells/EBV CD8	CDX552J7	%		Central memory EBV-specific cells / total EBV-specific cells
CCR7+CD45RA- EBV CD8 T Cells	CDX552C	10 ⁶ /L	Yes	[CDX552J7] * [EBVCD8] / 100
CCR7-CD45RA-EBV CD8+ Cells/EBV CD8	CDX553J7	%		Effector EBV-specific cells / total EBV-specific cells
CCR7-CD45RA-EBV CD8 T Cells	CDX553C	10 ⁶ /L	Yes	[CDX553J7] * [EBVCD8] / 100
CCR7-CD45RA+ EBV CD8+ Cells/EBV CD8	CDX554J7	%		Terminally differentiated effector memory EBV-specific cells / total EBV-specific cells
CCR7-CD45RA+ EBV CD8 T Cells	CDX554C	10 ⁶ /L	Yes	[CDX554J7] * [EBVCD8] / 100
CCR7+CD45RA+CXCR3+ EBV CD8+ Cell/EBV CD8	CDX546J7	%		Migratory Naive EBV-specific cells / total EBV-specific cells
CCR7+CD45RA+CXCR3+ EBV CD8 T Cells	CDX547C	10 ⁶ /L	Yes	[CDX546J7] * [EBVCD8] / 100
CCR7+CD45RA-CXCR3+ EBV CD8+ Cell/EBV CD8	CDX548J7	%		Migratory Central memory EBV-specific cells / total EBV-specific cells
CCR7+CD45RA-CXCR3+ EBV CD8 T Cells	CDX548C	10 ⁶ /L	Yes	[CDX548J7] * [EBVCD8] / 100
CCR7-CD45RA-CXCR3+ EBV CD8+ Cell/EBV CD8	CDX549J7	%		Migratory Effector EBV-specific cells / total EBV-specific cells
CCR7-CD45RA-CXCR3+EBV CD8 T Cell	CDX549C	10 ⁶ /L	Yes	[CDX549J7] * [EBVCD8] / 100
CCR7-CD45RA+CXCR3+ EBV CD8+ Cell/EBV CD8	CDX550J7	%		Migratory Terminally differentiated effector memory EBV-specific cells / total EBV-specific cells
CCR7-CD45RA+CXCR3+ EBV CD8 T Cells	CDX550C	10 ⁶ /L	Yes	[CDX550J7] * [EBVCD8] / 100

